**Adverse Event Reporting Description [\*]**

We will add relevant information about adverse event after finishing the study.

**Collection Approach for Table Default \*§**

- Systematic Assessment: The psychotherapist will routinely determine whether or not certain adverse events have occurred through regular investigator assessment during intervention and in each follow-up.
- Non-Systematic Assessment: Self-reporting by participants or occasional assessment by the psychotherapist.

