### Arm/Group Description \*§

**Intervention group:** Students will be intervened by an online 5-week professional identity group psychotherapy.

**Controlled group** will receive online messages of self-care knowledge forward by researchers.

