**3. Outcome Measures****Outcome Measure Information \***

A questionnaire will be used during each measurement, including several scales in it.

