**4. Adverse Event Information****Time Frame \*§**

The intervention lasts around 35 days, with 5 times, and we will record the adverse event at each time.

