**Adverse Event Term \***

The most possible adverse event may be the psychological discomfort because the participants. We will provide information for in two tables summarizing adverse events in each group, including serious adverse events, and other (not including serious) adverse events.

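### The psychotherapist's judgement is the only systematic source of harm data and no standard harm question is described for either group, so the by-group tables may under-count discomfort and compare unequally ascertained groups

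*Combined protocol and SAP*

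**What the plan says.** Section 4, Collection Approach for Table Default, sets out two routes for adverse events.

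- **Systematic:** "The psychotherapist will routinely determine whether or not certain adverse events have occurred through regular investigator assessment during intervention and in each follow-up".
- **Non-systematic:** "Self-reporting by participants or occasional assessment by the psychotherapist".

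Under Adverse Event Term the plan states: "The most possible adverse event may be the psychological discomfort". It promises "two tables summarizing adverse events in each group, including serious adverse events, and other (not including serious) adverse events". On timing, section 4 says: "The intervention lasts around 35 days, with 5 times, and we will record the adverse event at each time".

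Contact differs between the groups (section 1, Arm/Group Description). For Group A: "Students will be intervened by an online 5-week professional identity group psychotherapy". Group B "will receive online messages of self-care knowledge forward by researchers".

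Section 3 describes the data collection common to both groups: "A questionnaire will be used during each measurement, including several scales in it". The measurements are T0 and T1 (Outcome Measure Time Frame). The scales listed there are efficacy outcomes, and none is linked to adverse events.

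**The concern.** The expected harm is something a student feels, and the student is its primary source. The plan relies on self-report for all four of its scales, yet for an equally subjective harm its systematic source is another person's judgement. The student's own account is left to the route that, on the usual meaning of non-systematic, depends on someone volunteering it. The events to be looked for are not listed, and no checklist or standard question is given.

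A second problem concerns the comparison. The tables are by group, so they invite an A-B contrast. Group A takes part in psychotherapy sessions. No section says who assesses Group B, how, or when during the five weeks. A contrast between groups observed with different intensity mixes a difference in harm with a difference in looking.

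At stake is what the harm tables can be taken to mean. A low count could reflect little harm or little asking. A difference between groups could reflect the programme or the amount of contact.

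**Working it through.** The plan states no adverse-event rate, detection rate or precision target, so there is no figure of its own to reproduce. The only input from the documents is the group size: 55 in each group, 55 + 55 = 110 (section 1, Pre-assignment Details). The true rate *p* and the detected share *s* below are assumptions. Here *s* means the share of affected students recorded by **any** route, volunteered reports included. Students are treated as independent.

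**Formulas**

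- Expected recorded events per group = 55 × *p* × *s*
- Apparent A-B difference in percentage points, when the true rates are equal = 100 × *p* × (*s*A − *s*B)
- Chance that a group's table shows no event = (1 − *p* × *s*)^55

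**Step 1: absolute counts.** With *p* = 10%, 55 × 0.10 = 5.5 events are expected. With *s* = 30%, 55 × 0.10 × 0.3 = 1.65 are recorded; with *s* = 70%, 3.85 are recorded.

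With *p* = 5%, the chance of an empty table is:

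| Detection *s* | (1 − 0.05*s*)^55 |
|---|---|
| 100% | 0.060 |
| 70% | 0.141 |
| 50% | 0.248 |
| 30% | 0.436 |

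This applies to either group.

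**Step 2: the A-B contrast.** Take *p* = 20% in both groups, so 55 × 0.20 = 11 true events in each and no true difference:

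| Detection A | Detection B | Recorded A | Recorded B | Apparent A − B |
|---|---|---|---|---|
| 100% | 100% | 11 | 11 | 0 points |
| 50% | 50% | 5.5 | 5.5 | 0 points |
| 50% | 20% | 5.5 | 2.2 | +6 points |
| 80% | 20% | 8.8 | 2.2 | +12 points |
| 50% | 80% | 5.5 | 8.8 | −6 points |

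Over true rates of 5% to 30%, detection of 50% in A and 20% in B gives a spurious difference of +1.5 to +9 points against Group A. Detection of 50% in A and 80% in B gives −1.5 to −9 points, in its favour.

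**Step 3: what the documents fix.** They give neither *s*A nor *s*B. Step 1 shows that any incomplete detection lowers the counts. Step 2 shows that the sign of the between-group error depends on which group is observed better, and the plan does not settle that.

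**The case against.** A reader might infer something stronger: that discomfort felt but not shown goes unrecorded, that Group A's table is therefore biased low, and that the programme will look safer than it is. The documents do not support this, for four reasons.

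- **Self-report is collected.** It is a named route, and events are to be recorded at each of the five times. The psychotherapist's regular assessment may include asking each student; the text does not say. The defensible claim is a risk of under-recording.
- **Group B cannot be left out.** With only forwarded messages and no described psychotherapist contact, its events are at least as likely to be missed, which would make Group A look worse. The assessment at follow-up might be meant to cover both groups, but the plan does not say so.
- **The assessor's interest is an inference.** The psychotherapist presumably delivers the sessions and so knows the group, but no section says this. Nor does any section say that harm is assessed within the group session, so an argument from lack of privacy has no textual basis.
- **Other self-report exists.** Both groups complete the DASS-21 stress subscale at T0 and T1, and a general rating gathers feedback on the intervention. Distress could surface there.

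All four limit the claim, but none closes the gap. A route that depends on volunteering is not equivalent to asking everyone. If the assessment does include asking students, the plan should say so and say in which groups. The stress subscale is reported as a mean and standard deviation with no link to adverse events, so it does not identify students with an event.

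**Conclusion.** The concern holds in a limited form. The plan gives a subjective expected harm no systematic self-report, describes no standard harm question for either group, and leaves Group B's ascertainment undescribed. The counts in both groups may be too low, and the A-B contrast may be distorted by unequal ascertainment.

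The size is unknown. Under the assumed rates, the spurious differences illustrated run from −9 to +12 points, and the chance of an empty table at a 5% true rate rises from 6% with full detection to 14%–44% with detection of 70%–30%. These figures show sensitivity only; the plan offers nothing to choose among them. In particular, they do not show that Group A is favoured.

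The consequence is confined to the harm tables and what may be concluded from them. The efficacy outcomes and their analysis do not change. The point is worth acting on because the remedy uses an instrument both groups already complete.

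**What to change.** 1. In section 4, Collection Approach for Table Default, add student self-report as a systematic source. Put one short, fixed set of adverse-event items, covering the whole intervention period, into the T1 questionnaire, with identical wording in both groups.
2. In section 4, Adverse Event Term, base the between-group comparison on those items. Show psychotherapist-observed and volunteered events separately as a second source.
3. State whether the psychotherapist's assessment covers Group B, and whether it includes asking each student.
4. If the items are also asked during the intervention, ask both groups at the same times. The five recording occasions are tied to the intervention and no counterpart is described for Group B, so using them for Group A alone would add unequal ascertainment.

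**Cost:** a few more questionnaire items and small edits to two subsections, with no extra assessor. Asking once at T1 brings some recall error over about 35 days and misses students who do not reach T1, which is one reason to keep the second source. More mild events will be recorded, so the harm table will look slightly less favourable.

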**Adverse Event Term \***

The most possible adverse event may be the psychological discomfort because the participants. We will provide information for in two tables summarizing adverse events in each group, including serious adverse events, and other (not including serious) adverse events.

**Organ System \***

- Psychiatric Disorders

## **5. Limitations and Caveats**

The measurements are mostly based on self-reported scales and may lead to unreliable data. We will give instruction before fulfilling the questionnaire to ensure the participants understood.

## **6. Certain Agreements**

### **Are all PIs Employees of Sponsor? \***

- No: The principal investigator is not an employee of the sponsor

There is no agreement between the agent (university) and the principal investigators. The principal investigators are graduate students in the university. The principal investigators (PIs) can discuss the results of the study at a scientific meeting or any other public or private forum, or to publish in a scientific or academic journal information concerning the results of the study.

